6.6.3. Vital Signs

Vital sign data will be databased and available upon request.

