## 3. OBJECTIVES AND ENDPOINTS

Objectives	Endpoints
Primary: 

To compare the relative bioavailability of PF-07081532 following administration of a single oral dose of Formulation B (Test) compared to Formulation A (Reference) administered in the fasted state to adult participants who are overweight or obese.

	Primary: 

Plasma: PF-07081532 <math>AUC_{inf}</math> (as data permit, otherwise <math>AUC_{last}</math>) and <math>C_{max}</math> for Formulations A and B.

Secondary: 

To evaluate the safety and tolerability of a single oral dose of PF-07081532 administered in the fasted state to adult participants who are overweight or obese.

	Secondary: 

Assessment of treatment emergent AEs, clinical laboratory abnormalities, vital signs, ECG parameters.

Other: 

To determine additional pharmacokinetic parameters of PF-07081532 following administration of a single oral dose of PF-07081532 as Formulation A (Reference) and Formulation B (Test) in the fasted state to adult participants who are overweight or obese.

	Other: 

Additional plasma PK parameters:

<math>AUC_{last}</math>

<math>CL/F</math> and <math>V_z/F</math>, as data permit

<math>T_{max}</math>

Half-life (<math>t_{1/2}</math>), as data permit.

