### 9.3.2. Safety Analyses

All safety analyses will be performed on the safety population.

AEs, ECGs, BP, pulse rate, and safety laboratory data will be reviewed and summarized on an ongoing basis during the study to evaluate the safety of participants. Any clinical laboratory, ECG, BP, and pulse rate abnormalities of potential clinical concern will be described. Safety data will be presented in tabular and/or graphical format and summarized descriptively, where appropriate.

Medical history and PE and neurological examination information, as applicable, collected during the course of the study, will be considered source data and will not be required to be reported, unless otherwise noted. However, any untoward findings identified on physical

and/or neurological examinations conducted during the active collection period will be captured as AEs, if those findings meet the definition of an AE. Data collected at screening that are used for inclusion/exclusion criteria, such as laboratory data, ECGs, and vital signs, will be considered source data, and will not be required to be reported, unless otherwise noted. Demographic data collected at screening will be reported.

Additional specifications about the tables, listings, and figures will be outlined in the SAP.

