2.1. Modifications to the Analysis Plan Described in the Protocol

None.

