3.5. Safety Endpoints

The following data are considered in standard safety summaries (see protocol for collection days, baseline assessment, and list of parameters):

- adverse events (AE)
- laboratory data
- vital signs data
- electrocardiogram (ECG) results

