6.2. Secondary Endpoints

Analyses and summaries of safety data are described in [Section 6.6](#).

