6.6. Safety Summaries and Analyses

All safety analyses will be performed on the Safety Analysis Set.

Safety data will be presented in tabular and/or graphical format and summarized descriptively, where appropriate.

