6.6.4. Electrocardiograms

ECG data will be databased and available upon request.

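### SAP 6.6.3 and 6.6.4 plan no listing or summary of vital signs and ECG, although both are named parts of the secondary safety endpoint and SAP 2.1 declares no change from the protocol

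*SAP*

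**What the plan says.** Protocol section 3 defines the secondary endpoint as "Assessment of treatment emergent AEs, clinical laboratory abnormalities, vital signs, ECG parameters", and SAP 2.2 repeats it. For its analysis, SAP 6.2 says "Analyses and summaries of safety data are described in" Section 6.6. That section opens with a general statement: "Safety data will be presented in tabular and/or graphical format and summarized descriptively, where appropriate". Its subsections then differ. Adverse events are to be reported under the sponsor's standards (6.6.1), and laboratory data get a listing and a summary by treatment (6.6.2). For vital signs, 6.6.3 says only "Vital sign data will be databased and available upon request". For ECG, 6.6.4 says only "ECG data will be databased and available upon request".

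Protocol 9.3.2 states: "Any clinical laboratory, ECG, BP, and pulse rate abnormalities of potential clinical concern will be described". SAP 2.1, headed "Modifications to the Analysis Plan Described in the Protocol", records none.

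Other parts of the SAP assume that these outputs exist. SAP 3.5 begins "The following data are considered in standard safety summaries" and includes vital signs and ECG in the list that follows. SAP 5.3.2 gives a missing-value rule for standard summaries of both. SAP 3.5.3 and 3.5.4 set a predose Day 1 baseline for each period, and 3.5.4 gives the QTcF formula.

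**The concern.** A named endpoint component should have a planned output, and two of the four here have none. The contrast with the laboratory subsection immediately before them makes this read as a stated rule and not as missing detail. The rule conflicts with the protocol's commitment to describe abnormalities. It also conflicts with the SAP's own references to standard summaries, so a programmer cannot follow both sets of sections.

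What would be lost from the report is the numeric values, together with any value of potential clinical concern that the investigator did not judge to be an adverse event. The omission touches a risk the protocol itself names: section 2.3.1 lists increased heart rate and notes variable increases after single doses in the first-in-human study. Pulse rate and ECG heart rate are among the values with no planned output.

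**Working it through.** The point rests mainly on comparing text. The plan gives no figure of its own to reproduce.

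**Coverage of the endpoint**

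| Component (protocol 3, SAP 2.2) | SAP subsection | Planned output |
|---|---|---|
| Treatment-emergent AEs | 6.6.1 | Reported per sponsor standards |
| Laboratory abnormalities | 6.6.2 | Listing and by-treatment summary |
| Vital signs | 6.6.3 | None; kept in the database |
| ECG parameters | 6.6.4 | None; kept in the database |

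Two of four components have no dedicated listing or summary. The per-period baselines in SAP 3.5.3 and 3.5.4 feed no planned output.

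**How much data this concerns**

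Inputs:
- 20 participants, 10 per sequence (protocol Table 3), all assumed to complete both periods.
- Vital signs and ECG taken predose on Day 1 of each period, and on Day 5 in Period 2 only (SoA-Table 1 notes). Day 5 is about 96 h after the dose.
- Three vital sign parameters: systolic BP, diastolic BP, pulse rate.
- Five ECG parameters: QT, QTcF, PR, QRS, HR (SAP 3.5.4).

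Scheduled on-study readings, counted separately for vital signs and for ECG:
- Predose baselines: 20 × 2 = 40.
- In-period post-dose: 20 × 1 = 20.
- Total: 40 + 20 = 60.
- Post-dose per formulation: 20 / 2 = 10, since each sequence receives one formulation in Period 2.

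Post-dose values with no planned listing:
- Vital signs: 20 × 3 = 60.
- ECG: 20 × 5 = 100.

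Early termination readings would add to these. Because Day 5 readings exist only in Period 2, any comparison of formulations on them is between sequences and not within participant.

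**The case against.** The strongest reply is that the SAP was entitled to do this. Protocol 9.3.2 leaves the specification of tables, listings and figures to the SAP, and its presentation sentence is limited to what is appropriate, as is SAP 6.6. Protocol section 9 lets the SAP modify the plan and requires an amendment only for major changes to primary endpoints or their analyses. The commitment to describe abnormalities sits in a paragraph that begins with ongoing safety review, and narrative text in the report could meet it. Findings that meet the adverse event definition are reported anyway (protocol 8.3.2.1, Appendix 3; SAP 6.6.1), and protocol 8.3.3 has the site compare ECGs with the period baseline and repeat or escalate them. Finally, 20 readings at about 96 h say little about formulation differences, and the counts of 60 and 100 values all come from the same 20 visits.

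Much of this stands. The change is not prohibited, the gap is narrow and the data are few. The protocol does not itself require change-from-baseline listings or a by-treatment summary for these variables.

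It does not remove the conflict. Freedom to modify the plan does not make a declaration of no modification accurate, and the SAP names no place where the promised description would appear. The general sentence in 6.6 cannot be relied on when the specific subsections provide only for storage. If it was meant to govern, 6.6.3 and 6.6.4 are wrong. Adverse event reporting depends on investigator judgment and does not cover every value of potential clinical concern. Site ECG review protects participants but produces no report output. The same paragraph of protocol 9.3.2 also says, without qualification, that ECG, BP and pulse rate will be reviewed and summarized during the study, which favours the concern if anything.

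**Conclusion.** The concern holds. SAP 6.6.3 and 6.6.4 leave two of the four secondary endpoint components without a dedicated listing or summary. This conflicts with protocol 9.3.2 and with SAP 3.5 and 5.3.2, and SAP 2.1 does not declare it. The conflict is clear from the text and depends on no calculation. The data count assumes 20 completers and no early terminations.

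The consequence is modest: clinically significant abnormalities still reach the report as adverse events, nothing is lost from the database, and the PK analysis is unaffected. It should be corrected before the SAP is applied, chiefly because correction is so cheap.

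**What to change.** Replace SAP 6.6.3 and 6.6.4 with the following, on the Safety Analysis Set:

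1. A listing of vital sign and ECG values, including early termination readings, with change from the Period 2 Day 1 predose baseline to Period 2 Day 5. Add a short descriptive summary by treatment received in Period 2, with a statement that it compares sequences and not formulations within participant.
2. A listing or description of values of potential clinical concern. This is the part that protocol 9.3.2 directly requires. Protocol Appendix 8 can serve as the reference for ECG findings, noting that it lists alerts and is not exhaustive. For BP and pulse rate, cite the sponsor's reporting standards. The SAP cites these only for laboratory criteria (3.5.2), so the sponsor should confirm that they cover BP and pulse rate.

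If reduced reporting is intended, declare and justify it in SAP 2.1, say how the commitment in protocol 9.3.2 will be met, and align SAP 3.5 and 5.3.2. Changing the endpoint wording in SAP 2.2 alone would not do, because it repeats the protocol endpoint.

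The cost is SAP wording and a few standard outputs from data already collected.

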6.6.4. Electrocardiograms

ECG data will be databased and available upon request.

7. INTERIM ANALYSES

No formal interim analysis will be conducted for this study. As this is an open-label study, the sponsor may conduct unblinded reviews of the data during the course of the study for the purpose of safety assessment, facilitating PK/PD modeling, and/or supporting clinical development.

Final analysis will follow the official database release. As this will be an open-label study, there is no formal unblinding of the randomization code.

APPENDICES

Appendix 1. SAS Code for Analyses

An example of the PROC MIXED code is provided below:

For the primary objective:

```
proc mixed data=tab.pk;
  class seq period trt participant;
  model l&var = seq period trt/ ddfm=KR;
  random participant(seq) / subject=participant(seq);
  lsmeans trt;
  estimate 'B vs A' trt -1 1 /cl alpha=0.1;

  ods 'Estimates' out=est&var;
  ods 'lsmeans' out=ls&var;
  ods 'covparms' out=cov&var;
  ods 'tests3' out=tst&var;
run;

/* Letter assignments for treatments (trt) within the estimate statement above are as follows
A: PF-07081532 20 mg immediate release tablet + 60 mg immediate release tablet
(Reference);
B: PF-07081532 80 mg immediate release tablet (Test); */
```

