#### **4.2. Scientific Rationale for Study Design**

The Phase 2 clinical development program for PF-07081532 uses cold-storage immediate release tablets (Formulation A). A different, room temperature storage, immediate release formulation (Formulation B) is planned to be used in future clinical studies. Since the primary comparison of formulations in this study is between Formulations A and B, these formulations will be assessed in a cross-over manner in this study. These results will aid in identification of an equivalent dose to Formulation A for subsequent clinical studies where Formulation B is expected to be used. Consistent with the regulatory guidance, a single-dose design will be used in this study because these are generally more sensitive than steady-state studies in assessing the rate and extent of release of the drug substance from the drug product into the systemic circulation.

The results from the assessment of the effect of food on exposure indicate that PF-07081532 may be administered without regard to food (refer to IB). Inter-participant variability for PF-07081532 exposure after administration with food based on geometric %CV ranged from 12% to 29% for  $C_{max}$  and 28% to 34% for  $AUC_{inf}$ , and was comparable to the variability observed under fasted conditions. Thus, PF-07081532 will be administered in the fasted state, which is also consistent with the recommendation in the regulatory guidance for studies assessing relative bioavailability.

CCI

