#### **9.5. Sample Size Determination**

A sample size of 14 participants will provide adequate precision to estimate the relative bioavailability of PF-07081532. The following table presents the width of 90% CI for different estimated effects, with 80% coverage probability.

Parameter	Estimated Effect (100*Test/Reference)	90% CI		CI Width
AUC	85%	67.87%	106.45%	38.58%
	90%	71.86%	112.71%	40.85%
	95%	75.86%	118.97%	43.12%
	100%	79.85%	125.23%	45.39%
	105%	83.84%	131.5%	47.65%
	110%	87.83%	137.76%	49.92%
	115%	91.83%	144.02%	52.19%
C max	85%	74.47%	97.02%	22.54%
	90%	78.85%	102.72%	23.87%
	95%	83.23%	108.43%	25.20%
	100%	87.61%	114.14%	26.52%
	105%	91.99%	119.84%	27.85%
	110%	96.38%	125.55%	29.18%
	115%	100.76%	131.26%	30.50%

These estimates are based on the assumption that within-participant standard deviations are 0.291 and 0.171 for lnAUCinf and lnCmax, respectively, as obtained from study C3991001.

Participants who withdraw from the study or discontinue treatment, or whose PK samples are considered to be non-evaluable with respect to the primary PK objective may be replaced at the discretion of the investigator upon consultation with the sponsor.

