2.3. Study Design

This is a randomized, open-label, single dose, 2-period, 2-sequence, crossover study. Participants will be screened for participation in this study within 28 days before dosing in Period 1 to confirm that they meet the inclusion/exclusion criteria for this study. A minimum washout of 6 days between the single 80 mg doses (80 mg immediate release tablet for Formulation B, 20 mg immediate release tablet + 60 mg immediate release tablet for Formulation A) administered in each period will be employed. The expected duration of participation from Screening to the Follow-up telephone contact will be approximately 10 weeks.

Approximately 20 participants will be enrolled to ensure at least 14 evaluable participants with PK data.

Table 2. Randomization Schedule

	Period 1	Period 2
Sequence 1 (N=10)	Formulation A	Formulation B
Sequence 2 (N=10)	Formulation B	Formulation A

Formulation A (Reference) will be administered as PF-07081532 20 mg immediate release tablet + 60 mg immediate release tablet, and Formulation B (Test) will be administered as a PF-07081532 80 mg immediate release tablet.

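### SAP Appendix 1's example code leaves the participant variance bounded at zero, so the nominal 90% CI can cover slightly under 90% in the long run and need not use the n-2 df behind Section 9.5

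*SAP*

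**What the plan says.** SAP 6.1 and Protocol 9.3.1.1 specify a mixed model on the log scale with sequence, period and treatment fixed and participant within sequence random. The treatment difference and its 90% CI are back-transformed to a ratio. SAP Appendix 1 gives example code for this. It has the random statement "random participant(seq) / subject=participant(seq"), requests Kenward-Roger df and a 90% interval, and puts no option on the procedure statement beyond the data set. Neither document says what happens if the participant variance is estimated as zero.

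Protocol 9.5 states: "A sample size of 14 participants will provide adequate precision to estimate the relative bioavailability". Its table "presents the width of 90% CI for different estimated effects, with 80% coverage probability", assuming that "within-participant standard deviations are 0.291 and 0.171" for lnAUCinf and lnCmax. SAP 2.3 adds: "Approximately 20 participants will be enrolled to ensure at least 14 evaluable participants with PK data".

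Protocol 4.2 reports that, after dosing with food, the inter-participant "geometric %CV ranged from 12% to 29" per cent for Cmax and 28% to 34% for AUCinf, and that this "was comparable to the variability observed under fasted conditions".

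SAP 5.1 states that no hypothesis is tested. Neither document sets an acceptance range.

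**The concern.** In a complete 2x2 crossover, the treatment contrast is normally judged against within-participant variation alone, on n-2 df. A variance bounded at zero breaks this whenever the between-participant mean square happens to be the smaller. The model then drops the participant effect and pools both mean squares on twice the df. The pooled value is below the within-participant mean square and the t quantile is smaller, so the interval is always shorter than the n-2 df interval.

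This is usually a rare event in crossover trials, because participants differ much more from each other than from themselves. Here, the AUC figures in Protocol 4.2 and 9.5 are close enough that it may not be rare. With no hypothesis test, the ratio and its 90% CI are the trial's only inferential result, and Protocol 4.2 says they will help to match the dose of Formulation B to that of Formulation A. The interval should therefore have its stated coverage and the error basis on which its precision was planned.

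**Working it through.** **1. Reproduce the Protocol 9.5 table.** Log half-width = t(0.95, df) × SDw × √(2/14) × √(χ²(0.80, df)/df). With df = 12 this is:

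- AUC: 1.782 × 0.291 × 0.378 × 1.148 = 0.225, giving 79.85% to 125.23% at a ratio of 100%, as printed.
- Cmax: 0.225 × 0.171/0.291 = 0.132, giving 87.61% to 114.14%, as printed.

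The 85% and 115% rows also match. For AUC at 100%, 13 df gives 80.04-124.94 and 24 df gives 81.15-123.22; neither matches. The table therefore rests on the within-participant residual with n-2 df.

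**2. What the bound does.** Take 14 complete participants, 7 per sequence. There are 28 observations and 4 fixed-effect parameters. MSW and MSB, the within- and between-participant mean squares, each have 12 df, with expectations sw² and sw² + 2sb². If MSB < MSW, bounded REML sets sb² = 0, and the residual becomes (MSW + MSB)/2 on 28 - 4 = 24 df. The t quantile falls from 1.782 to 1.711. Direct REML fits to six simulated data sets confirmed the zero estimate and the pooled residual.

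**3. How large is sb²?** Read the CV as total spread: total log variance = ln(1 + CV²), and sb² = total - sw².

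- AUC, sw² = 0.291² = 0.0847. CV 28%: 0.0755 - 0.0847 = -0.009. CV 34%: 0.1094 - 0.0847 = 0.025.
- Cmax, sw² = 0.171² = 0.0292. CV 12%: 0.0143 - 0.0292 = -0.015. CV 29%: 0.0808 - 0.0292 = 0.052.

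Negative values are set to zero below unless stated.

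**4. Frequency and coverage.** P(bound hit) = P(F(n-2, n-2) < sw²/(sw² + 2sb²)). Coverage comes from simulation (1 to 2 million draws per case): MSW and MSB are scaled χ² variables with n-2 df, and the treatment estimate is normal with variance 2sw²/n. For AUC at n=14:

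| CV (total) | sb² | Bound hit | Mean half-width if hit: bounded / 12 df | Coverage if hit: bounded (12 df) | Coverage if not hit | Overall coverage |
|---|---|---|---|---|---|---|
| 28% | 0 | 50% | 0.1862 / 0.2143 = 0.87 | 90.0% (93.8%) | 86.1% | 88.1% |
| 31% | 0.007 | 40% | 0.1917 / 0.2185 = 0.88 | 90.9% (94.3%) | 87.3% | 88.7% |
| 34% | 0.025 | 22% | 0.2025 / 0.2275 = 0.89 | 92.6% (95.3%) | 88.5% | 89.4% |

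The intervals are thus 11-13% narrower on average when the bound is hit. The 12-df interval covers 90.0% overall because over-coverage where MSW is large offsets under-coverage where it is small. The bound removes part of that offset. In the first row: 0.50 × 90.0 + 0.50 × 86.1 = 88.1.

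Other cases:

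- AUC, n=20: bound hit in 17-50% of trials, overall coverage 88.4-89.6%.
- Cmax, n=14: 50% and 88.1% (CV 12%); 19% and 89.5% (CV 20%); 0.7% and about 90% (CV 29%).
- AUC, n=14, taking sb² = -0.009 literally: bound hit in 66%, overall coverage 87.1%, and 88.4% among the trials that hit it.

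**5. Alternative reading.** If the CV is pure between-participant variance, then at n=14 the bound is hit in 2-4% of trials for AUC and 0.1-13% for Cmax, with coverage of 89.7-90.0%.

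**6. With the variance unbounded.** Coverage is 90.0%, and the 80th-percentile AUC interval at 100% is 79.85-125.24, in line with Section 9.5. With the bound it is 81.60-122.55 (sb² = 0) to 80.58-124.11 (CV 34%).

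**The case against.** The strongest objection is that a reader might infer that, once the bound is hit, the reported interval is itself too narrow. The figures do not support that. Across the AUC range with sb² at or above zero, those intervals cover 90.0-92.6%, because such trials tend to have a large within-participant mean square. They fall below 90% only if two measurements on the same participant are truly negatively correlated. The loss belongs to the procedure's overall coverage. This objection stands.

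A reader might also infer that the plan's own figures make the event likely. That depends on reading Protocol 4.2's inter-participant CV as total variance. Read as pure between-participant variance, the event is uncommon and almost harmless. The subtraction is also fragile. It combines estimates that carry their own error, the CVs are for fed dosing, and at a Cmax CV of 12% the implied intraclass correlation is about -1.05, which is impossible. This stands as a limit on how firmly the frequency can be stated.

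Further, a planning table does not bind the analysis to 12 df, and with up to 20 participants the df will differ anyway. That is fair for the number 12. It does not answer the point that the table's error basis is the within-participant residual on n-2 df, while under the bound the basis depends on which mean square happens to be larger.

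Finally, the code is labelled an example, it matches the stated model, and a random participant effect with Kenward-Roger df is a legitimate choice. All true: the gap is one unstated option, not a wrong model.

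**Conclusion.** This is a minor point, worth fixing because the fix is nearly free. On the total-variance reading, long-run coverage of the nominal 90% CI is about 88.1-89.4% for AUC at n=14 (88.4-89.6% at n=20), and from 88.1% to about 90% for Cmax at n=14. On the pure between-participant reading the effect is negligible. The documents do not settle which reading applies.

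The result assumes PROC MIXED's default bounding, complete data with equal sequences, and the within-participant SDs in Section 9.5. It would be tempting to conclude that a formulation conclusion could flip. The documents do not support that: there is no hypothesis and no acceptance range, so no formal decision changes.

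**What to change.** Add the NOBOUND option to the PROC MIXED statement in SAP Appendix 1, and state in SAP 6.1, before analysis, how a zero or negative participant variance estimate is handled. Complete data then always give the within-participant residual with n-2 df, as in Section 9.5, and the stated model is kept. Fitting participant(seq) as a fixed effect gives the same result with complete data, but departs from the random effect specified in Protocol 9.3.1.1 and SAP 6.1.

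The cost is one option and one sentence. The downside is that a negative participant variance estimate may be printed and will need a footnote. With complete data the point estimate does not change. Incomplete participants would alter the df under either approach.
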